## Objectives

The purpose of this study is to assess the effect of education as a determinant for hepatitis-C related literacy rate and improvement in decision-making capacity in patients with current or past history of hepatitis C who are currently on opiate replacement therapy.

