## Hypothesis

We anticipate better outcomes in literacy and decision-making capacity with more interactive intervention i.e. video educational session as compared to education delivered via a brochure.

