## Scientific Endpoints

### Response:

As a result of participation in the interactive educational sessions, we aim to demonstrate

1. Improved health literacy in Opioid Agonist Treatment (OAT) patients
2. Improved decision making among OAT patients

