## Study Design

We will start with a retrospective chart review to extract information about patient demographics, which will include age, gender, race/ethnicity, educational status, marital status, and history of mental health problems, information about substance abuse & status of hepatitis C, occupational and employment status. Some of this information will be required to decide matching factors between the clinics.

We will employ an observational two-group method design to evaluate the effect of video or computer-based education as a determinant of seeking treatment for HCV among patients on opioid agonist therapy (OAT). Group A will receive the video class intervention on the computer administered by an on-site facilitator, while “group-B” will receive an HCV educational brochure. The two groups are matched in 1:1 fashion to make the two groups similar with respect to the certain key characteristics, such as race, sex, age etc. The outcome variable is the percentage of the individuals in the two groups that retain HCV-knowledge. We expect up to 2-3 clinics to participate.

These intervention will occur after pre-test assessment by a designed questionnaire, which will include questions from different aspects of hepatitis-C infection disease process. Patients will not be notified of their questionnaire score. We will assess the questionnaires reliability and accuracy among a patient sample drawn from the clinics where the questionnaires will be deployed. We will also convey a committee of experts who will provide input on the design of the educational intervention. The last step before analysis will be post interventional assessment with the same questionnaire used for pre-intervention assessment. At the end of the study, we plan to utilize the data for analysis and manuscript preparation.

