## **Procedures Involved**

We plan to conduct a study involving 2 groups. One group consists of the intervention subjects and other of the control subjects. The intervention subjects will receive the computer-based video education, while the “control group” will receive the brochure-based intervention. The goal is to evaluate the effect of education on health literacy in people with hepatitis C and currently on opiate replacement therapy. We also plan to evaluate the willingness for treatment in people with active hepatitis C infection.

We will start with a feasibility survey to assess the patient demographics at all clinic sites where this study will be conducted. We will also conduct cognitive testing of the survey instruments to be administered to ensure reliability and accuracy. We will also request that patient partners and subject matter experts provide guidance on the educational intervention to be delivered. The study flyers for advertisement will be distributed at all the clinic sites. Patients will be given information about the study. In case of agreement to participate, informed consent will be obtained. After enrollment of the population of interest, we will start the retrospective chart review in order to extract information about patient demographics, which will include age, gender, race/ethnicity, educational status, marital status, and a history of mental health problems, information about substance abuse & status of hepatitis C, occupational and employment status.

After that information is collected, we plan to designate the population in 2 groups i.e. Intervention & Control. The next step will be the educational intervention in group A which will consist of distribution of HCV educational brochure. Similarly group B will have the video class intervention on the computer administered by an on-site facilitator. These interventions will occur after the pre-test assessment by a designed questionnaire which will include questions on different aspects of hepatitis-C infection disease processes. Finally, we will administer a post interventional assessment with the same questionnaire used for pre-intervention assessment. For patients with history of HCV infection irrespective of treatment, an additional section will be added to check their willingness for treatment.

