| | |
|------------------------------|---|
| Official Title: | Hepatitis C-Video vs. Brochure Education Delivery |
| NCT number: | NCT04204447 |
| Document Type: | Statistical Analysis Plan |
| Date of the Document: | June 30, 2018 |

Statistical Methods

We will initiate the activities on this study with collection of patient demographics at all sites. As part of the preparatory work, we will conduct cognitive testing of the survey instruments to be administered to ensure reliability and accuracy.

The population will be designated into 2 groups i.e. Intervention & Control. The intervention will have the video class intervention and the control will read an HCV educational brochure. We will design both interventions to assess the level of HCV knowledge. Information provided by the brochure and the video will be assessed by the pre/post test questions. These interventions will occur after the pre-test assessment by a designed questionnaire which will include questions on different aspects of hepatitis-C infection disease processes. The last step before analysis will be post interventional assessment with the same questionnaire used for pre-intervention assessment administered 1 month (+/- 2 weeks) after the intervention. All of the intervention and assessment tools will be validated before use. The second assessment may be done over the phone if the subject has no scheduled visits to the clinic during the follow-up period.

At the end we do plan to utilize the data for analysis and manuscript preparation.

Description of the clinics: The two clinics are approximately the same in terms of the percentage of rural patients, of rural HCV seropositive patients, and in the gender distribution. Because patient characteristics differ on the basis of age, race, and ethnicity, we will perform 1:1 matching of the subjects, if possible from the two clinics on these variables.

Statistical analysis: We will conduct exploratory data analysis using box plots for comparison between distributions of continuous variables. Histograms also will provide an additional way of comparing these distributions. Continuous variables are going to be summarized by means and standard deviations or medians and interquartile range, as appropriate. Discrete, that is, categorical variables will be summarized by proportions.

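### The objective, first endpoint and goal claim an effect of education on HCV literacy, but both arms are educated and retested with the same questionnaire, so at most video versus brochure can be estimated

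*Protocol*

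**What the plan says.** Three places in the protocol frame the aim as an effect of education, with no comparator named:

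- Objectives: "The purpose of this study is to assess the effect of education as a determinant for hepatitis-C related literacy rate".
- Procedures Involved: "The goal is to evaluate the effect of education on health literacy in people with hepatitis C".
- Scientific Endpoints: "As a result of participation in the interactive educational sessions, we aim to demonstrate", followed by the first endpoint, "Improved health literacy in Opioid Agonist Treatment (OAT) patients".

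Other places are comparative. The Hypothesis sets the "video educational session as compared to education delivered via a brochure". The Background describes the plan as studying different ways of delivering education. Study Design defines the outcome as the percentage in each of the two groups that retains HCV knowledge. The SAP's title sets video against brochure.

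On the arms, the SAP (Statistical Methods) says: "The intervention will have the video class intervention and the control will read an HCV educational brochure". On measurement, Procedures Involved has a "post interventional assessment with the same questionnaire used for pre-intervention assessment". The SAP repeats this and places the second assessment 1 month after the intervention, give or take 2 weeks. Study Design adds that patients are not told their scores. Neither document describes an untreated, delayed or attention-control group, an alternate form of the questionnaire, or any correction for retesting.

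**The concern.** An objective worded as the effect of education asks what would have happened to knowledge without it. No group here shows that. The control group is a second educated group, and everyone has already seen the items when they answer them again.

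A participant's score can rise between the two assessments for reasons other than the study material: the items are familiar, the pre-test prompted the participant to look up answers, or ordinary clinic care supplied HCV information during the month. All of these are absorbed into the change from pre-test to post-test.

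What is at stake is the claim the report may make. The objective, first endpoint and goal are the statements a report is written against, and nothing in either document limits how a rise in score is to be interpreted. A report that answered them literally could credit education with a rise that would have occurred had neither material taught anything.

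**Working it through.** **1. What the design identifies.** Write the mean pre-to-post change in arm j as

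G_j = E_j + R_j,

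where E_j is the effect of that arm's education and R_j is the change that would have occurred anyway. If R is common to both arms:

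- G_video = E_video + R
- G_brochure = E_brochure + R

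That is two observed quantities and three unknowns. The difference G_video − G_brochure = E_video − E_brochure is identified, because R cancels. Neither E_video nor E_brochure is identified, and the pooled change, (E_video + E_brochure)/2 + R for equal arms, still contains R. If R differs between arms, the difference is biased by R_video − R_brochure.

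**2. The plan's own figure.** The SAP (Power/Sample Size) gives 81 per group for a difference of 0.20, 80% power and significance level 0.05. It states no base rate. Searching multiples of 0.05 from 0.05 to 0.70 with the two-sided pooled-variance formula, only 0.20 reproduces the whole table to within rounding. For 0.20 versus 0.40 (mean 0.30):

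n = [1.960·√(2·0.30·0.70) + 0.842·√(0.20·0.80 + 0.40·0.60)]² / 0.20² ≈ 81.2.

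So 81 reproduces. It is sized on attendance at a first appointment, however, not on knowledge scores. It is used below only as a plausible arm size and does not bear on step 1.

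**3. Illustration of size.** Inputs:

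- n = 81 per arm (SAP).
- Pre-post correlation ρ = 0.6, equal SDs, true education effect zero, normal approximation. All are assumptions; the documents give no score SD, correlation or expected gain.
- Retest gain g = 0.1, 0.2 or 0.3 SD (assumption).

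SE of the mean change = √(2(1 − ρ)/n) = √(0.8/81) = 0.0994 SD.

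The chance that a two-sided 0.05 paired test in one arm is significant is Φ(g/SE − 1.96) + Φ(−g/SE − 1.96):

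| Retest gain (SD) | g/SE | ρ = 0.6, one arm of 81 | ρ = 0.5 to 0.7, one arm | ρ = 0.5 to 0.7, both arms pooled (162) |
|---|---|---|---|---|
| 0.1 | 1.01 | 0.172 | 0.15 to 0.21 | 0.25 to 0.38 |
| 0.2 | 2.01 | 0.521 | 0.44 to 0.64 | 0.72 to 0.91 |
| 0.3 | 3.02 | 0.855 | 0.77 to 0.94 | 0.97 to 0.999 |

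Under the same assumptions, with R common, the between-arm test keeps its 0.05 error rate.

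**4. Is such a test planned?** None is named. The only score comparison the SAP specifies (Statistical analysis) is between a post-intervention assessment and a 1-month follow-up. Its Statistical Methods text describes a single post-intervention assessment, at 1 month, so the number and timing of assessments are themselves unclear. The rates in step 3 therefore describe a test that the wording of the aims invites, not one that the plan schedules.

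**The case against.** The strongest reply is that the study is already comparative. The Hypothesis, the Background, the two-group outcome in Study Design, the between-group power calculation and the SAP's title all point to a comparison. The endpoint's reference to interactive sessions can be read as meaning the video, since the Hypothesis uses the same adjective for it. On that reading, what remains is loose wording in Objectives and Procedures Involved. Much of this stands: the aims are mixed, and the video-versus-brochure hypothesis escapes the problem. But the objective and goal name no comparator, and the first endpoint asks for improvement rather than a difference. That inconsistency is the point.

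A second reply is that withheld scores and a gap of about a month reduce retest effects. They may, but they cannot show how much change is left, and a month also leaves time for outside information.

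Some stronger readings are tempting and should not be drawn:

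- A reader might infer that the plan will test pre-to-post gain and report it as caused by education. No such test is named.
- A reader might add regression to the mean. Eligibility rests on age, suboxone therapy and language, not on a pre-test score, so no shift in the group mean is expected from selection.
- A reader might count the study flyers as a source of learning. They are advertisements, listed before consent and hence before the pre-test, and nothing says they carry HCV content.

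**Conclusion.** The point holds as a mismatch between the stated claim and the design. As designed, the trial cannot establish that education improved HCV literacy, whether from one arm's change or from both arms pooled. That conclusion follows from having two educated arms and no group retested without education; it needs no assumption about the size of a retest gain.

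The 17%, 52% and 85.5% figures are illustrations. They depend on the assumed correlation, retest gains and zero education effect, on an arm size taken from a different endpoint, and on a test the documents do not name. They should not be read as the error rate of a planned analysis.

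The comparison in the Hypothesis survives on two conditions. First, the retest effect must be the same in both arms. Second, clinic must not account for the difference. The SAP refers to the clinic that receives the brochure and plans to match subjects across the two clinics. This suggests, without stating it, that allocation is by clinic, so video versus brochure may be confounded with clinic.

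**What to change.** Reword three statements in the protocol so that each names the difference between video and brochure in HCV knowledge: the aim in Objectives, the first endpoint in Scientific Endpoints, and the goal in Procedures Involved. This brings them into line with the Hypothesis and the Background.

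Add one sentence, in the protocol and the SAP: pre-to-post change within an arm, or pooled over arms, is descriptive and will not be reported as an effect of education.

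The cost is wording only; no data, visits or participants are added. The downside is a narrower claim, since the trial would no longer set out to show that education itself raises literacy.

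It may be tempting to recover that claim by repeating the questionnaire in the preparatory sample, of which Study Design says: "We will assess the questionnaires reliability and accuracy among a patient sample drawn from the clinics where the questionnaires will be deployed". I would not rely on that. The sample's size is not stated, it is planned for reliability and cognitive testing rather than a scored retest, and as a non-concurrent group it would be a weak reference for the two arms.

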## Hypothesis

We anticipate better outcomes in literacy and decision-making capacity with more interactive intervention i.e. video educational session as compared to education delivered via a brochure.

## Scientific Endpoints

### Response:

As a result of participation in the interactive educational sessions, we aim to demonstrate

1. Improved health literacy in Opioid Agonist Treatment (OAT) patients
2. Improved decision making among OAT patients

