To understand the impact of clinic and individual patient characteristics on the HCV seropositive individuals, we will begin with building logistic regression models. If the outcome variable is defined as "1" when an HCV seropositive individual is identified and "0" otherwise, logistic regression will provide the association of HCV seropositivity as a function of clinic and individual characteristics. Further, to understand the changes in these percentages over time, we will perform a trend analysis at the minimum.

We will test the differences between the scores obtained on the post-intervention assessment and the 1-month follow up assessment. We will assess the distribution of the scores. Modeling will be done using generalized linear mixed-effects models or an alternative appropriate approach. We will include demographic factors and other covariates as appropriate.

Power/Sample Size:

The following table shows the sample size needed per group, as a function of the difference in the proportion of patients from both clinics who appear for the first appointment and the desired power of the test. The level of significance is 0.05.

| Differences in proportions | Power | |
|----------------------------|-------|------|
| | 0.80 | 0.90 |
| 0.10 | 293 | 392 |
| 0.15 | 138 | 184 |
| 0.20 | 81 | 108 |

| | | |
|------|----|----|
| 0.25 | 54 | 72 |
| 0.30 | 39 | 51 |

Thus, if our difference is 20% between those who make the first appointment for an HCV evaluation in the clinic that receives the SAMHSA brochure and the full education groups, we will need 81 patients per group (total 162) to have an 80% power.

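### Decision making is one of two endpoints and half of the hypothesis, but its measurement is not defined and the SAP specifies no analysis of it.

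*Protocol*

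**What the plan says.** Three places in the Protocol commit the trial to this construct. Objectives names "hepatitis-C related literacy rate and improvement in decision-making capacity in patients with current or past history of hepatitis C". Hypothesis says "We anticipate better outcomes in literacy and decision-making capacity with more interactive intervention", comparing video with brochure. Scientific Endpoints lists two items: health literacy, and "Improved decision making among OAT patients".

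After that list the term does not return. Study Design names one outcome: "The outcome variable is the percentage of the individuals in the two groups that retain HCV-knowledge". The pre/post questionnaire is described, in both documents, as covering aspects of the HCV disease process.

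Two related items appear elsewhere:

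- Procedures Involved states an aim of evaluating willingness for treatment. For patients with a history of HCV, "an additional section will be added to check their willingness for treatment".
- The SAP's Power/Sample Size section is built on the proportion of "those who make the first appointment for an HCV evaluation". It asks for 81 per group (162 in total) for 80% power at a 0.20 difference and a 0.05 significance level.

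The SAP's planned analyses are descriptive summaries, a logistic regression of HCV seropositivity on clinic and patient characteristics with a trend analysis, and a mixed-effects or alternative model of assessment scores.

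**The concern.** An endpoint needs a measure, a time point, a population and an analysis. Endpoint 2 has only a name. If the plan is followed exactly, the final report can say nothing about whether video beats brochure on decision making, although the hypothesis says it will. If the gap is filled later, the measure can be chosen after the data have been seen.

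The word improved also implies either a change from baseline or a fair contrast between arms. The groups are matched rather than randomised, and the SAP matches on age, race and ethnicity only where possible. If willingness were asked only after the intervention, a raw comparison would carry over any difference in willingness that existed at the start.

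The sample size has a related problem. It is justified by an outcome that the rest of the plan neither collects nor analyses.

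**Working it through.** **Step 1. Set each candidate measure against what an endpoint needs.**

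| | Willingness section | First HCV appointment |
|---|---|---|
| Where it appears | Protocol, Procedures Involved | SAP, Power/Sample Size only |
| Linked to decision making in the text? | No | No |
| Population | Patients with HCV history | Patients from both clinics; need for an evaluation not addressed |
| Time point | Not stated | No window stated |
| Collection procedure | Added questionnaire section; no scoring | None described |
| Analysis in the SAP | None | None |

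Endpoint 2 refers to OAT patients in general. Objectives describes patients with current or past hepatitis C, whereas Inclusion and Exclusion Criteria require age, suboxone therapy and English, with no HCV history. The population for the endpoint is therefore unsettled too.

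**Step 2. Check the planned models.** The logistic model has seropositivity as outcome and clinic and individual characteristics as predictors. The score model compares assessment scores. Neither is said to take willingness, attendance or decision making as its outcome.

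**Step 3. Reproduce the SAP's own sample size.** The inputs given are a difference d = 0.20, significance 0.05 and power 0.80. The base rate and sidedness are not given. Assume two-sided, 20% vs 40%, 1:1, pooled normal approximation:

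n = [z₀.₉₇₅√(2p̄(1−p̄)) + z₀.₈₀√(p₁(1−p₁)+p₂(1−p₂))]² / d²

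With p̄ = 0.30: n = [1.960 × 0.6481 + 0.8416 × 0.6325]² / 0.04 = [1.2702 + 0.5323]² / 0.04 = 81.2, against 81 stated. At this base rate every cell of the table is reproduced to within one patient. An arcsine formula at base 0.20–0.21 and a one-sided continuity-corrected formula at base 0.27–0.29 also fit the table closely. The base rate and sidedness therefore cannot be read off with certainty.

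**Step 4. Power for a 20-point difference, shown as a range.** Using the same approximation:

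power = Φ{[0.20√n − 1.960√(2p̄(1−p̄))] / √(p₁(1−p₁)+p₂(1−p₂))}

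Example at 20% vs 40%, n = 81: (1.800 − 1.2702) / 0.6325 = 0.838, so power is 0.799. The share is the assumed fraction of each group of 81 that contributes to the endpoint.

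| Base rate | Share 100% (n = 81) | Share 75% (n = 60.75) | Share 50% (n = 40.5) |
|---|---|---|---|
| 5% | 0.953 | 0.880 | 0.720 |
| 10% | 0.897 | 0.794 | 0.618 |
| 20% | 0.799 | 0.676 | 0.502 |
| 30% | 0.743 | 0.616 | 0.450 |
| 40% | 0.725 | 0.599 | 0.435 |

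The base rates and shares are assumptions; the documents give neither. The table treats the endpoint as binary with a 20-point difference. The SAP assumes that difference for attendance, not for willingness.

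**The case against.** The fairest reply is that the construct is loosely connected rather than absent. Background speaks of motivating patients to pursue HCV evaluation and treatment. Study Design calls education a determinant of seeking treatment. Procedures Involved plans a willingness section, and the power calculation uses appointment attendance. Together these suggest what the sponsor had in mind.

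That reply rules out three stronger readings:

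- A reader might infer that decision making is never measured. The documents do not support this: a willingness section is planned, and the questionnaire itself is not reproduced, so relevant items in it cannot be excluded. What can be said is that none is described.
- A reader might infer that willingness has no baseline. The section is mentioned directly after the post-test, but that post-test is said to use the same questionnaire as the pre-test. The timing is unstated, so a baseline is neither planned nor ruled out.
- A reader might infer a definite loss of power because only some patients have an HCV history. If enrolment follows Objectives, all patients have that history and there is no such loss. The loss arises only if enrolment follows the eligibility list. Its size also depends on an unstated base rate and on carrying the attendance difference over to willingness, whose scale is not given.

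None of this supplies a definition of endpoint 2 or an analysis of it. The documents never designate either proxy as the measure.

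**Conclusion.** The point holds as a gap in definition and analysis: one of two stated endpoints gets no between-arm estimate under the plan as written. This rests on the text alone and needs no numerical assumption. Knowledge, the other endpoint, is unaffected by this point, so the plan should be corrected but the trial is not undermined as a whole.

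Power is secondary and should be quoted only as an assumption-based range. With 81 per group, a 20-point difference and a two-sided test, it is about 73%–95% if all patients contribute, 60%–88% if 75% do, and 44%–72% if 50% do, for base rates of 40% down to 5%.

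**What to change.** 1. Designate attendance at the first HCV evaluation appointment, the outcome already used for the sample size, as the measure of endpoint 2.
2. Collect it by a record look-up after the intervention, within a fixed window stated in advance. The chart review now described covers patient characteristics, so this is an additional step. Confirm first that the appointments are recorded where study staff can see them.
3. State the denominator, either all patients or only those with an HCV history, and reconcile Objectives with Inclusion and Exclusion Criteria. The share of patients who contribute follows from this choice.
4. Analyse attendance with a separate logistic model containing study arm, the matching variables and baseline covariates. Leave the seropositivity model as it is; putting a new outcome into it would give no arm comparison, because it names no arm term. The SAP's power text suggests that one clinic receives the brochure. If arm coincides with clinic, state that the two effects cannot be separated.
5. Ask the willingness section at both pre-test and 1 month, define its scoring, and compare arms adjusting for the pre-test answer as a supportive analysis.
6. State the base rate and sidedness behind the sample-size table.

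The alternative is to remove decision making from the objective, hypothesis and endpoints.

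The cost is wording in both documents, one extra record look-up per patient and a few more items at pre-test.
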